Nivolumab is minimally myelosuppressive and should be easily combined with ICE salvage chemotherapy. Since nivolumab is an immunotherapy that may provide a stronger response in patients who are immunocompetent, we would like to examine its efficacy in the pre-AHCT population. We propose a sequential study of using nivolumab as 1st salvage therapy post induction failure. For patients who achieve CR, they can go directly to AHCT. For patients not in CR after 12 weeks of nivolumab or who have not achieved at least a PR after 6 weeks of nivolumab, we will combine nivolumab plus ICE for 2 cycles. Patients achieving a SD at the end of the first 6 weeks of single agent nivolumab can be allowed to continue with nivolumab alone at the physician/investigator's discretion on a case-by-case basis. This approach is meant to increase the proportion of patients who are in CR at the time of AHCT.

During the progress of Cohort B, prior to the formal assessment of safety, we have observed promising efficacy in this group of high-risk patients with primary refractory or early relapsed HL treated thus far (CR in all, n = 13). In this group salvage regimens are often associated with lower CR rates in patients with primary refractory cHL compared to relapsed cHL^{9,10}. Therefore, with poorer outcomes after both conventional and even more novel immunotherapy-containing regimens, improving the efficacy of salvage therapy remains critical in patients with high-risk cHL. Given the exceptionally high CR rate observed thus far and without any signals of excess toxicity to date, we will expand Cohort B to a full Phase 2 efficacy cohort to assess whether the CR rate after 3-4 cycles of therapy (Nivolumab x 1, Nivolumab+ICE x 2-3) in high-risk patients is promising compared to historical data.

Objectives:

In Hodgkin lymphoma patients with relapsed or primary refractory disease post induction chemotherapy:

Primary:

Evaluate the anti-tumor activity of nivolumab as single agent and in combination with ICE chemotherapy (NICE) as assessed by complete response (CR) rate prior to autologous hematopoietic cell transplantation.

Secondary:

- 1) Assess the safety and tolerability of nivolumab ± ICE chemotherapy through evaluation of toxicities, including type, frequency, severity, attribution, time course and duration.
- 2) Obtain estimates of overall response rate (ORR), response duration and survival (overall and event-free).

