New Cohort (B): Due to the high CR rate with nivolumab alone, only a small number of patients have been treated with NIVO + ICE thus far. Based on the small number of patients treated with NIVO + ICE, it is not possible to adequately characterize the full spectrum of toxicities with NIVO + ICE, nor is it possible to obtain an adequate preliminary estimate of the anti-tumor efficacy. Therefore, a separate cohort has been added to the study, which will be enrolled after the completion of the original PET-adapted cohort. In this new cohort, all patients will receive a cycle of nivolumab and then NIVO + ICE x 2-3 cycles. **Updated April 27, 2021:** Given the exceptionally high CR rate observed thus far and without any signals of excess toxicity to date, we will expand Cohort B to a full Phase 2 efficacy cohort to assess whether the CR rate after 3-4 cycles of therapy (Nivolumab x 1, Nivolumab+ICE x 2-3) in high-risk patients is promising compared to historical data. Implementing a Simon two-stage minimax design, we plan to enroll and treat a minimum of 19 and a maximum of 35 patients at the Cohort B schedule in order to discriminate a promising CR rate of 74% from a disappointing response rate of 50% using a type I error rate of 0.05 and power of 90%. At stage 1, 19 patients will be entered on the study (which includes the n=13 patients treated thus far in Cohort B), therefore we expect to enroll only 22 new patients on the Cohort B phase 2 trial portion of the study to count toward the 35 patients required. If ≤ 9 complete responses are seen, the study will be terminated. If at least 10 patients achieve CR, the trial will continue to the second stage. At stage 2, 16 additional patients will be entered. At the end of stage 2, if 23 or more patients experience complete response, the combination will be considered worthy of further study. If ≤ 22 patients achieve a complete response then no further investigation of the combination is warranted.

Endpoints:

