During the progress of Cohort B, prior to the formal assessment of safety, we have observed promising efficacy in the patients treated thus far (CR in all, n = 13). This is outstanding efficacy in a particularly high-risk group of patients with primary refractory or early relapsed HL. To provide context for these results, the efficacy of conventional platinum- or gemcitabine-based chemotherapy regimens is similar, with ORR and CR rates by PET ranging between 70- 89% and 54-73%, respectively^{3,9,58,61-63}. Achievement of a complete metabolic response (CMR) prior to transplant is a critical prognostic factor for auto-HCT outcome⁶⁴⁻⁶⁷. Several studies incorporating BV and/or PD-1 blockade into initial salvage therapy have aimed to improve the CMR rate prior to auto-HCT. Sequential and combination BV-based salvage regimens have been studied^{10,14,68-74}. Although a minority of patients will have a CR with BV alone as initial salvage therapy (27-43%)^{68,69}, the CMR rates after sequential BV-chemotherapy or combined BV/chemotherapy range from 68-76%. BV (1.8 mg/kg) and nivolumab (3 mg/kg) combined as initial salvage therapy q3 weeks for 4 cycles (n=91) yielded an ORR of 85% and CR rate of 67%⁷⁵ with excellent durability of responses (3-year PFS of 77% in all patients). However, among high-risk patients who had primary refractory HL after frontline therapy, salvage regimens are often associated with lower CR rates in patients with primary refractory cHL compared to relapsed cHL, including some chemotherapy regimens (BeGeV: 59% refractory vs 84% relapsed)⁹, BV+chemo regimens (BV+bendamustine: 64% refractory vs 84% relapsed)¹⁰, and BV+Nivo (48% refractory vs 71% relapsed). Notably, the 3-year PFS in patients with primary refractory cHL versus relapsed cHL after BV+nivolumab as first salvage therapy was 61% in primary refractory cHL versus 90% in patients with relapsed cHL.

Therefore, with poorer outcomes after both conventional and even more novel immunotherapy-containing regimens, improving the efficacy of salvage therapy remains critical in patients with high-risk cHL. Given the exceptionally high CR rate observed thus far and without any signals of excess toxicity to date, we will expand Cohort B to a full Phase 2 efficacy cohort to assess whether the CR rate after 3-4 cycles of therapy (Nivolumab x 1, Nivolumab+ICE x 2-3) in high-risk patients is promising compared to historical data.

3 Patient Eligibility

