Cohort B: Due to the high CR rate with nivolumab alone, only a small number of patients have been treated with NIVO + ICE thus far. Based on the small number of patients treated with NIVO + ICE, it is not possible to adequately characterize the full spectrum of toxicities with NIVO + ICE, nor is it possible to obtain an adequate preliminary estimate of the anti-tumor efficacy. Therefore, a separate cohort has been added to the study, which will be enrolled after the completion of the original PET-adapted cohort. In this new cohort, all patients will receive a cycle of nivolumab and then NIVO + ICE x 2-3 cycles. We plan to enroll and treat 18 eligible patients in this new cohort. The sample size is based on assessing unacceptable toxicities with NIVO + ICE. With 18 patients, we can estimate the proportion of patients experiencing unacceptable adverse events with sufficient precision (standard error ≤ 0.12 , half width ≤ 0.23).

Updated April 27, 2021:

Given the exceptionally high CR rate observed thus far and without any signals of excess toxicity to date, we will expand Cohort B to a full Phase 2 efficacy cohort to assess whether the CR rate after 3-4 cycles of therapy (Nivolumab x 1, Nivolumab+ICE x 2-3) in high-risk patients is promising compared to historical data. See full rationale provided in Section 2.5.

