The phase 2 portion will implement a Simon two-stage minimax design^{15,87} to evaluate the anti-lymphoma activity of the two-agent combination as assessed by CR rate, in patients with high-risk HL. The Cohort B phase 2 portion is expected to enroll and treat a minimum of 19 and a maximum of 35 patients at the Cohort B schedule. The sample size is based on the desire to discriminate a promising CR rate of 74% from a disappointing response rate of 50%³ using a type I error rate of 0.05 and power of 90%. At stage 1, 19 patients will be entered on the study. Note: The n=13 patients treated thus far as part of the safety evaluation portion of the study will count toward the 35 patients required; given this, we expect to enroll only 22 new patients on the Cohort B phase 2 trial. If ≤ 9 complete responses are seen, the study will be terminated. If at least 10 patients achieve CR, the trial will continue to the second stage. At stage 2, 16 additional patients will be entered. At the end of stage 2, if 23 or more patients experience complete response, the combination will be considered worthy of further study. If ≤ 22 patients achieve a complete response then no further investigation of the combination is warranted.

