12.2 Sample Size Accrual Rate

Assuming 1) nivolumab and NIVO + ICE are well tolerated and 2) the study does not close for futility, 43 evaluable patients will be enrolled on the phase II portion of the study. Study enrollment will be complete within 24 months from activation (accrual of 1-2 participants per month). Expected accrual for the safety monitoring segment: n=6.

Sample Size, Cohort B: We plan to enroll and treat 18 eligible patients. With 18 patients, we can estimate the proportion of patients experiencing unacceptable adverse events with sufficient precision (standard error ≤ 0.12 , half width ≤ 0.23). Expanded Sample Size (Anti-Lymphoma Activity): The Cohort B phase 2 portion is expected to enroll and treat a minimum of 19 and a maximum of 35 patients at the Cohort B schedule.

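### Cohort B: the 13/13 complete responses that prompted the Simon design also count in it, so the stage 1 stop and the minimum of 19 no longer describe the remaining trial, and Section 12.4 plans no CR estimate in the new patients

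*Combined protocol and SAP*

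**What the plan says.** Cohort B was first sized at 18 patients, to estimate the proportion with unacceptable toxicity (Sections 12.1.1 and 12.2). Section 2.5, in its April 2021 update, then reports that "we have observed promising efficacy in the patients treated thus far (CR in all, n = 13"), and the synopsis places this observation "prior to the formal assessment of safety, we have observed promising efficacy in this group of high-risk patients". Section 12.1.1 gives the reason for turning the cohort into an efficacy study: "Given the exceptionally high CR rate observed thus far and without any signals of excess toxicity to date, we will expand Cohort B". Section 2.5 adds the poor outcomes of high-risk disease as a further reason.

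The added design is a Simon two-stage minimax design for a CR rate of 74% against 50%, "using a type I error rate of 0.05 and power of 90" per cent. It stops at 9 or fewer CRs in 19. "If at least 10 patients achieve CR, the trial will continue to the second stage", with 16 more patients, and 23 or more CRs in 35 is success.

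The carry-over of the first 13 is disclosed. Section 12.1.1 says "The n=13 patients treated thus far as part of the safety evaluation portion of the study will count toward the 35 patients required" and expects 22 new patients. The synopsis puts the 13 inside stage 1: "At stage 1, 19 patients will be entered on the study (which includes the n=13 patients treated thus far in Cohort B"). Section 12.2 says that the phase 2 portion "is expected to enroll and treat a minimum of 19 and a maximum of 35 patients at the Cohort B schedule"; the synopsis and Section 12.1.1 give the same range.

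For analysis, Section 12.4 plans the percentage of evaluable patients with confirmed CR and a 95% Clopper-Pearson interval. It does not separate the first 13 from later patients.

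**The concern.** A two-stage design offers two things here: a chance to stop early if the regimen looks poor, and error rates that hold when no outcome is known at the start. In Cohort B, 13 outcomes were known, all were CRs, and that result is a main stated reason for the test.

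Two consequences are not spelled out anywhere. First, stage 1 needs 10 CRs and 13 were already reported. A site, ethics board or monitoring committee reading the synopsis or Section 12.1.1 would take it that the new patients enter a trial that may stop for lack of efficacy after 19. Second, the only planned CR estimate contains the run of responses that led to the expansion. A striking early run tends to overstate the true rate, and a pooled figure carries that overstatement into the result.

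**Working it through.** **Inputs.** p0 = 0.50, p1 = 0.74, n1 = 19, stage 1 stop at 9 or fewer, N = 35, success at 23 or more (Section 12.1.1 and synopsis); 13 CRs in 13 patients (Section 2.5); new patients 35 − 13 = 22, of whom 19 − 13 = 6 complete stage 1 and 16 form stage 2.

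**The plan's own figures.** With X1 ~ Bin(19, p) and X2 ~ Bin(16, p), P(success) = Σ over x = 10 to 19 of P(X1 = x) · P(X2 ≥ 23 − x).
- At p = 0.50: 0.0444. At p = 0.74: 0.9004.
- P(stop at stage 1) = P(X1 ≤ 9) = 0.500 at p = 0.50 and 0.012 at p = 0.74.
- Expected N at p = 0.50: 19 + 0.500 × 16 = 27.
- A search over two-stage designs for these inputs returns 9/19, 22/35 as the minimax design.

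The stated design therefore reproduces.

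**Stage 1 as it now stands.** With 13 CRs counted, 0 of 6 in the remaining stage 1 patients still gives 13/19, above the boundary of 10. The chance of an efficacy stop is 0 at any true rate. If only k of the 13 CRs are confirmed, stage 1 fails when the 6 new patients give at most 9 − k CRs:
- k ≥ 10: impossible.
- k = 9: P(0 of 6) = 0.016 at a rate of 50%.
- k = 8: P(at most 1 of 6) = 0.109 at 50%.

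So at least 4 of the 13 must be reclassified before the stop could act.

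**Final rule as it now stands.** Success needs 23 − 13 = 10 CRs in 22 (45.5%). Given 13/13, P(Y ≥ 10) with Y ~ Bin(22, p) is 0.738 at 50%, 0.945 at 60% and 0.999 at 74%. The 50% figure must be read with the fact that 13/13 itself has probability 0.50^13 = 0.0001 at that rate.

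**Pooled estimate.** Given 13/13, the expected pooled rate is (13 + 22p)/35, so the expected excess over the new patients' rate p is 13(1 − p)/35.

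| True rate p in new patients | Expected pooled rate | Excess, points | P(13/13) at p |
|---|---|---|---|
| 74% | 83.7% | 9.7 | 0.020 |
| 80% | 87.4% | 7.4 | 0.055 |
| 90% | 93.7% | 3.7 | 0.254 |

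Given 13/13, the pooled exact 95% interval covers p with probability 0.862, 0.845 and 0.999 at these rates; the exact interval from the 22 alone covers with at least 0.97. Without conditioning, the 35-patient interval covers at 0.96 to 0.98.

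**At the success boundary.** Pooled 23/35 = 65.7% (47.8% to 80.9%); the same outcome in the new patients is 10/22 = 45.5% (24.4% to 67.8%).

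**The case against.** Much of this is open to a careful reader. The plan says that the 13 count, that all had CR, that the boundary is 10, and that 22 new patients are expected. The synopsis lists 35 for Cohort B. Passing stage 1 early is also normal: at a true rate of 74%, 10 CRs are reached within the first 13 patients with probability 0.55. The futility rule was met by data, not switched off. This stands, and it reduces the first consequence to text that describes a stage already passed.

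The 13/13 result is itself strong evidence. Its exact 95% lower limit is 75.3%, above the 74% called promising, and eligibility and schedule are the same for the new patients. The loss of a 0.50 chance of stopping at a rate of 50% is therefore a remote scenario. This also stands.

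The excess and coverage figures condition on exactly 13/13. If 11/13 would also have led to expansion, the average excess across triggering results would be smaller. The documents do not say what result would have sufficed, so the figures are an upper case.

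Oversight remains. Section 12.3 halts accrual for toxicity. Section 16.3 has the management team discuss response and the appropriateness of further enrolment, though with no numeric efficacy rule. Section 12.4 is a general plan and does not forbid a separate estimate.

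A reader might infer that the type I error is really 74%. The documents do not support this. The 0.738 is conditional on a result that almost never occurs at a 50% rate; over all outcomes the rule gives 0.044. Because the test was prompted by the data, 5% is not guaranteed, but no violation is shown.

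**Conclusion.** The point holds, as one of description and estimation. Provided at least 10 of the 13 CRs stand at the evaluable, confirmed level of Sections 11.1 and 12.4, the stage 1 boundary was met before any new patient entered. The stop at 9 of 19 and the minimum of 19 do not describe the trial that remains. Enrolment is expected to reach 35 unless the toxicity halt or a management team decision intervenes. With all 13 confirmed, the outcome turns on 10 CRs in 22.

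The cut-offs, sample size and design-stage error rates are sound. The success decision is a count, so it does not rest on the estimate. The estimate still shapes how the regimen's activity is judged. Given 13/13, the pooled rate is expected to overstate the new patients' rate by up to 9.7 points at 74%, falling to 3.7 at 90%, and no planned analysis shows the rate free of the triggering run. The text should be corrected and the estimate added; neither change alters the design.

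**What to change.** Keep 9/19, 22/35 and N = 35 as the decision rule.

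1. In Sections 12.1.1 and 12.2 and the synopsis, replace the minimum of 19 with a statement that the 13 carried-over patients already met the stage 1 boundary, subject to confirmation of their CRs. Add that no efficacy futility stop is expected and that 35 is the expected size. Label 5% and 90% as design-stage values. State that success now needs at least 10 CRs in the 22 new patients (23 minus the confirmed count, if fewer than 13 stand). Do not set conditional probabilities beside the 5% as if they were error rates.

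2. In Section 12.4, prespecify a supportive CR rate with exact 95% interval in the Cohort B patients not among the 13 (expected 22), reported beside the pooled 35. Define the group by exclusion of the 13, since the data cut-off for that count is not given. State that it is an estimate and not a second success criterion.

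The cost is a few sentences and one extra interval, with no new data. The downside is width: the half-width is about 0.2, for example 28.2% to 71.8% at 11/22 and 59.7% to 94.8% at 18/22.

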12.2 Sample Size Accrual Rate

Assuming 1) nivolumab and NIVO + ICE are well tolerated and 2) the study does not close for futility, 43 evaluable patients will be enrolled on the phase II portion of the study. Study enrollment will be complete within 24 months from activation (accrual of 1-2 participants per month). Expected accrual for the safety monitoring segment: n=6.

Sample Size, Cohort B: We plan to enroll and treat 18 eligible patients. With 18 patients, we can estimate the proportion of patients experiencing unacceptable adverse events with sufficient precision (standard error ≤ 0.12 , half width ≤ 0.23). Expanded Sample Size (Anti-Lymphoma Activity): The Cohort B phase 2 portion is expected to enroll and treat a minimum of 19 and a maximum of 35 patients at the Cohort B schedule.

12.3 Safety Analysis and Stopping Rules for Excessive Toxicity

Following the *patient safety monitoring segment*, the early stopping rule for safety/toxicity will continue to be assessed for each patient after cycle 1. The expected rate of unacceptable toxicity should not be $\geq 33\%$. See **Section 5.2** for unacceptable toxicity definition. This rule is in addition to the quarterly review of all toxicities submitted to the COH DSMC. Given the number of patients treated, if the unacceptable toxicity rate is $\geq 33\%$, patient accrual will be halted and a full review of the data by the Data Safety Monitoring Committee (DSMC) will be mandated.

Cohort B: The early stopping rule for safety/toxicity will be assessed for each patient after C2, which is the first cycle of NIVO+ICE combination therapy.

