5.2 Definition of Unacceptable Toxicity

Unacceptable toxicity in a given patient is defined as any hematologic or non-hematologic grade 3/4 toxicity that does not resolve to a grade 1/2 within 14 days per NCI CTCAE v4.03 toxicity criteria and is considered at least possibly related to nivolumab and/or NIVO + ICE, or any other regimen-related cause of death.

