Study Design Characteristics: This phase II trial will implement a Simon Two-Stage Optimal Design¹⁵ to evaluate the anti-lymphoma activity of NIVO± ICE chemotherapy. The trial is expected to enroll a minimum of 15 and a maximum of 43 subjects. The sample size is based on the desire to discriminate a promising CR rate of 70% from a disappointing CR rate of 50% (a rate below what can be achieved with ICE/augmented ICE) using a type I error rate of 0.05 and power of 80%. At stage 1, 15 subjects will be entered on the study. If ≤ 8 complete responses are seen, the study will be terminated. If at least 9 subjects achieve a CR, the trial will continue to the second stage. At stage 2, 28 additional subjects will be entered. At the end of stage 2, if 27 or more subjects experience a complete response, the combination will be considered worthy of further study. If ≤ 26 subjects experience a complete response then no further investigation of the regimen is warranted.

Safety Monitoring Segment: NIVO is already FDA approved for treatment of HL and thus does not require special safety monitoring. Since the combination of nivolumab and ICE has not been tested before, the trial will include a 6-patient safety monitoring cohort for patients treated with nivolumab plus ICE (cycle 1). If $\leq 1/6$ patients experience unacceptable toxicity, then the study will continue. If 2 or more patients experience unacceptable toxicity, we will stagger the dose of nivolumab and ICE by 1 week so that nivolumab will start on day 1 and ICE will start on day 8 of a 21 day cycle. There will then be another 6 patient cohort added to the monitoring. If $\leq 1/6$ patients experience unacceptable toxicity in the staggered cohort, then the study will continue. If, however, 2 or more patients experience unacceptable toxicity in the staggered cohort, then nivolumab will not be given in combination with ICE.

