14.2 Reporting of Adverse Events

14.2.1 Routine Recording of Non-Serious Adverse Events

Routine AE recording will occur via data entry into the study eCRF. Recording of adverse events will begin once the patient is consented and will continue until 100 days after discontinuation of dosing. Adverse events will be monitored by the Protocol Management Team (PMT). Adverse events that do not meet the criteria of serious OR are not unanticipated problems do not require expedited reporting. AEs reported

through expedited processes (i.e. reported to the IRB, DSMC, FDA, etc.) must also be reported in routine study data submissions.

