14.2.2 Expedited Reporting Requirements of SAEs and UPs to the COH Regulatory Committees

Adverse Events that meet the criteria of serious OR are unanticipated problems will be reported according to the approved [City of Hope Clinical Research Adverse Event and Unanticipated Problem policy](#).

Reporting of SAEs will begin after the patient signs the study consent, and must be followed until the event is resolved, stabilized, or determined to be irreversible by the participating investigator. Follow-up SAE reports must be submitted for all events that require expedited reporting when the status of the event changes and until the resolution or stabilization of the event. For ongoing reportable adverse events that are unrelated to study agent, the follow-up period may end at the 30-days post study-drug assessment.

Non COH Sites:

Serious Adverse Events meeting the criteria specified in the City of Hope Clinical Research Adverse Event and Unanticipated Problem policy will be reported to the Data Coordinating Center (DCC) and Study PI within **24 hours** of notification that the event occurred.

Procedure for reporting SAEs/UPs to the COH DCC

1. Sites are to report to their local IRB per their site's specific institutional and IRB guidelines. As soon as possible, non-COH sites will provide to the COH DCC copies of the IRB submission and corresponding IRB response.
2. Document/describe the SAE/UP on each of the following:
 - a. MedWatch 3500A: Downloadable form at <http://www.fda.gov/medwatch/getforms.htm>
 - b. UP/SAE Coversheet (Appendix B): A modifiable Microsoft Word document is available from the DCC. An electronic signature on the document will be accepted.
3. Scan and email above documents to [contact] and [contact] with the subject title as "COH IRB 16403 SAE". If an email receipt from Coordinating Center personnel is not received within one working day, please email [contact].

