16.3 Protocol Management Team (PMT)

The Protocol Management Team (PMT) minimally consisting of the study principal investigator, collaborating investigators, site investigators, research nurse, clinical research associate/coordinator, and the study biostatistician is responsible for ongoing monitoring of the data and safety of this study, including implementation of the stopping rules for safety/toxicity.

The PMT is recommended to meet (in person or via teleconference) to review study status. The meeting is a forum to discuss study-related issues including accrual, SAE/AE/UPs experienced, study response, deviations/violations and study management issues. The appropriateness of further subject enrollment and the specific intervention for subsequent subject enrollment are addressed.

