16.5 Risk Determination

This is a High Risk study as defined in the [City of Hope Institutional DSMP](#). This determination was made because the study involves a COH IND.

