Appendix E: Supplemental Materials

These documents are relevant to the protocol; however, they are not considered part of the protocol. They are stored and modified separately; therefore, modifications to these documents do not require protocol amendments.

City of Hope Data and Safety Monitoring Plan

City of Hope's Institutional policy: 05/14/14] Titled: Reviewing and Reporting Unanticipated Problems and Adverse Events Involving Risk to Research Participants or Others

Clinical Research Protocol Deviation policy

Charter for the Data And Safety Monitoring Committee (DSMC)

COH IRB 16043Clinical Monitoring Plan

COH Office of Clinical Trial Auditing and Monitoring SOP

COH DCC Operations Manual – this document will serve as guidance as to the responsibilities of the Data Coordinating Center, as well as those of the participating sites (for this study specifically).

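### The only automatic safety halt on accrual (12.3) counts a regimen-related death as one event toward a 33% rate, so the protocol text requires no pause after a first such death

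*Combined protocol and SAP*

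**What the plan says.** Section 5.2 defines unacceptable toxicity as a treatment-related grade 3/4 event that has not come down within 14 days, "or any other regimen-related cause of death". A death and a prolonged toxicity therefore carry the same weight. Section 12.3 refers to that definition and sets a cumulative limit: at a rate of 33% or more among patients treated, "patient accrual will be halted and a full review of the data by the Data Safety Monitoring Committee (DSMC) will be mandated". In Cohort B the rule is assessed for each patient after C2, the first NIVO+ICE cycle.

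The other stopping provisions do different work. The 6-patient safety segment in 12.1.1 staggers the schedule at 2 or more events and, if that recurs, drops the combination; it does not halt accrual. The Simon stage 1 stop is for futility.

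The protocol does require reporting and review after a death:

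- Section 14.2.2: serious events from non-COH sites "will be reported to the Data Coordinating Center (DCC) and Study PI within" 24 hours.
- Section 14.2.1: events reported "through expedited processes (i.e. reported to the IRB, DSMC, FDA, etc.) must also be reported in routine study data submissions".
- Section 14.2.4.1: unexpected fatal events go to the FDA within 7 calendar days.
- Section 14.2.4.3: for reportable serious events the study PI informs participating investigators within 30 days and states whether the protocol or consent must change.
- Section 12.3: the DSMC reviews all toxicities quarterly.
- Section 16.6: safety questions are taken up with the Protocol Management Team (PMT). Section 16.3 says of its meetings: "The appropriateness of further subject enrollment and the specific intervention for subsequent subject enrollment are addressed".

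Section 16.5 adds: "This is a High Risk study as defined in the" institutional data and safety monitoring plan (DSMP). Appendix E lists that plan, the DSMC charter and the policy on unanticipated problems and adverse events, and says: "These documents are relevant to the protocol; however, they are not considered part of the protocol".

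**The concern.** A first regimen-related death is the event after which a required stop for review is most useful, and a pooled 33% rate is a poor detector of it. A bar that high can suit prolonged grade 3/4 toxicity under ICE. It is far above any death rate that would be tolerable in patients being bridged to a potentially curative transplant.

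Two features of the trial make this more than formal. Section 12.1.1 justifies the safety segment with the words "Since the combination of nivolumab and ICE has not been tested before". Section 2.5 records that the decision to expand Cohort B came before its formal safety assessment, although it also reports no sign of excess toxicity in the first 13 patients. Followed literally, the stated rule would let enrollment continue through several regimen-related deaths unless someone chose to stop it.

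**Working it through.** **Inputs**

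- Threshold: 33% of patients treated (12.3).
- Cohort B: 13 treated at the April 2021 update, maximum 35, so 35 - 13 = 22 new patients (12.1.1).
- Accrual: 1-2 patients per month (12.2).
- Unacceptable toxicities among the 13: not stated. I take x = 0 to 2 as the main range. x = 3 (3/13 = 23.1%) sits poorly with the report of no excess toxicity and is a sensitivity case.
- Regimen-related death rate on NIVO+ICE: not stated. I assume 1% and 2%. Section 2.2.4 reports no drug-related grade 4 or 5 events in the phase I nivolumab trial in Hodgkin lymphoma and no drug-related grade 5 events in the phase II trial, both of monotherapy. Section 6.2 warns of fatal infections with ifosfamide. Rates of 5% and 10% are sensitivity cases only.

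**1. The plan's own figures.** 2/6 = 33.3%, so the 33% limit agrees with the safety-segment rule. The precision stated for 18 patients also reproduces: SE = sqrt(0.5 × 0.5 / 18) = 0.118 and half width = 1.96 × 0.118 = 0.231. The plan gives no operating characteristics for the halt itself.

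**2. Deaths needed to trigger the halt, with the 13 in the denominator.** Find the smallest k with (x + k)/(13 + k) ≥ 0.33, where k consecutive new patients die.

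| Prior events x | One death | Last value without a halt | Halt at |
|---|---|---|---|
| 0 | 1/14 = 7.1% | 6 deaths, 6/19 = 31.6% | 7 deaths, 7/20 = 35.0% |
| 1 | 2/14 = 14.3% | 4 deaths, 5/17 = 29.4% | 5 deaths, 6/18 = 33.3% |
| 2 | 3/14 = 21.4% | 3 deaths, 5/16 = 31.3% | 4 deaths, 6/17 = 35.3% |
| 3 | 4/14 = 28.6% | 1 death, 4/14 = 28.6% | 2 deaths, 5/15 = 33.3% |

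Consecutive deaths are the case most favorable to the rule. Event-free patients in between raise the denominator and can only push the trigger further away.

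**3. The other reading of the denominator.** Section 12.3 does not say whether the 13 count. On the 22 new patients alone, a lone death triggers the halt only if it falls among the first 3 (1/3 = 33.3%; 1/4 = 25.0%).

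**4. How often a death-triggered pause would occur.** P(at least one death in 22) = 1 - (1 - p)^22. At p = 0.01 this is 1 - 0.802 = 0.198; at p = 0.02 it is 1 - 0.641 = 0.359. Sensitivity: about 68% at 5% and 90% at 10%. Expected qualifying deaths at 1% and 2% are 22p = 0.2 and 0.4.

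**5. How often a second death would follow.** P(at least 2 deaths in 22) = 1 - (1 - p)^22 - 22p(1 - p)^21 = 2.0% at 1% and 7.1% at 2% (sensitivity: 30% at 5%, 66% at 10%). Counting deaths only, with 0-2 prior events, the probability that the 33% rule halts accrual rounds to 0.000 at 1% and 2%. These figures therefore reflect the assumed death rate, and the rule has almost no influence on them.

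**6. Time scale.** At 1-2 patients per month, one quarter between DSMC reviews is 3-6 further starts if nobody intervenes. Each week of pause defers about 0.2-0.5 of an enrollment.

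**The case against.** The strongest reply is that the protocol already responds to a death. Reporting is prompt, the study PI must state within 30 days whether the protocol or consent has to change, the DSMC reviews toxicity quarterly, and the PMT has the question of further enrollment in its remit. The PMT or the DSMC may stop accrual at any time. This stands, and it narrows the point to one gap: accrual is not suspended while those steps run. It does not close the gap, because section 16.3 only recommends that the PMT meet and the quarterly cycle is long relative to enrollment.

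Second, the institutional DSMP, the DSMC charter or the adverse event policy to which 14.2.2 sends serious events may already require a pause. That stands too. Only the silence of the protocol text is shown here.

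Third, the second-death probabilities are driven by assumed rates, and the large values need 5-10%, which nothing in the documents supports. Agreed; the structural result in step 2 needs no death rate.

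Fourth, a trigger with no time limit would catch late deaths in earlier patients, who stay in survival follow-up under 5.5, and would cause more pauses than step 4 shows. That is a fair criticism of an open-ended rule, and it is why the proposed sentence has a time window.

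Finally, this is a design preference, and no endpoint or analysis is in error. True, but the change would alter what happens to patients, so it is more than a request for detail.

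**Conclusion.** This is a cheap improvement. Within the protocol text, 12.3 is the only automatic safety halt on accrual, and for deaths it hardly ever acts. With the 13 in the denominator and 0-3 prior events, a first death as the only new event cannot trigger it. With 0-2 prior events it takes 7, 5 or 4 consecutive deaths. This rests on the stated threshold and on the assumed count of prior events, which the documents do not give.

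Three stronger readings are tempting and not supported. A reader might infer that a death would go unreviewed; sections 12.3, 14 and 16 show otherwise. A reader might infer that the trial as conducted has no pause rule; the institutional documents that could contain one are not available here. A reader might take the second-death probabilities as deaths that a pause would prevent. They are not: a pause does nothing for patients already on treatment, and it helps later patients only if the review changes something.

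**What to change.** Add one sentence to 12.3: *Any death at least possibly related to nivolumab or NIVO+ICE that occurs during protocol treatment or within 100 days of the last dose pauses accrual until the DSMC has reviewed it.* If an institutional rule already does this, cite it there instead. Leave the 33% rule and the 5.2 definition as they are, with deaths still counted in the numerator.

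The pieces exist: attribution as possible is defined in 14.1, adverse events and SAEs are already collected to 100 days (14.2.1, 14.2.4.2), and the DSMC is in place. The Cohort B toxicity endpoint and the sample size do not change.

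The cost is an amendment and short pauses, whose length depends on how quickly the DSMC meets. The chance of at least one over the 22 new patients is about 20% or 36% at assumed death rates of 1% or 2%. Any of the first 13 patients still inside the 100-day window would add slightly to this. The sentence does not settle whether the 13 belong in the 12.3 denominator; the same amendment could say so.
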